### 5.5. Rationale for Amendment (e)

Due to recent changes in the FDA ertlotinib label and National Comprehensive Cancer Network (NCCN) Guidelines, the Sponsor amended the protocol to address the impact on study enrollment completion, and the need for a larger improvement in OS than that historically targeted for NSCLC patients. In addition, OS is considered the preferred primary endpoint for regulatory approval and hence PFS is removed from the primary objective so all statistical power can be reallocated to enhance the success for OS. The amendment updates include the followings:

- PFS is removed as a co-primary endpoint and changed to a secondary endpoint. With this change OS becomes the sole primary endpoint.
- The final OS analysis will occur when approximately 304 OS events have been observed, a reduction from the current protocol requirement of 407 OS events. With this change, the study will provide 80% statistical power for a new targeted hazard ratio of 0.72.
- Due to the reduced number of targeted OS events, a smaller sample size of approximately 450 patients will be sufficient to reach the 304 OS events for the final analysis (note that current protocol requires 550 patients).

While amending the protocol, the Lilly study team remains blinded to aggregate data and will not be unblinded until the final OS analysis per Section 9.5.

Previously, erlotinib was indicated for the treatment of patients with locally advanced or metastatic NSCLC after failure of at least 1 prior chemotherapy regimen (Tarceva® United States [US] package insert [USPI], 2010) based upon the BR-21 study. In addition, NCCN Guidelines (April 2015) supported erlotinib use as an option for subsequent second line or third line treatment in NSCLC patients (all histologies) for PS 0-3.

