# 9.5. Blinding

This is a randomized, open-label study. Randomization will occur using an interactive web response system. Assignment to treatment groups will be determined by a computer-generated random sequence. Each patient in this study will be aware of his or her own assigned treatment group. At each investigative site, all staff involved in treating and caring for study patients will have full knowledge of treatment assignments for the patients under their care.

In order to maintain the scientific integrity of this trial, access to study data will be strictly controlled prior to the interim and final analyses. For the accumulated group-level data, treatment assignment will not be included, and other parameters that can disclose treatment assignment will be scrambled. Therefore, the sponsor and all investigative sites will remain

blinded to treatment group assignments for the summary statistics and reports until the database lock for the final analysis. Scrambled treatment assignments will be used in the reporting database for Lilly trial-level safety review until the final database lock. Interim analyses will be carried out approximately every 6 months by an independent DMC (external to Lilly) to monitor safety and efficacy. The DMC is unblinded and the Statistical Analysis Center (SAC), which is also external to Lilly, will carry out analyses for the DMC. Until the primary analyses, only the SAC and the DMC will be unblinded to the summary statistics and reports.

For the interim PK analysis to occur prior to the interim/primary analyses, the list of individuals that will have access to unblinded data will be provided with the PK/PD analysis plan, and documentation concerning their access to the data will be retained.

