# 12. Sample Size and Statistical Methods

### 12.1. Determination of Sample Size

The primary objective of this study is to compare abemaciclib versus erlotinib with respect to OS in patients with Stage IV NSCLC whose tumors have detectable *KRAS* mutations (specifically, in codons 12 and 13 of the *KRAS* oncogene) and who have progressed after prior platinum-based therapy and received 1 other prior therapy or are not eligible for further chemotherapy.

The study will enroll approximately 450 patients in 3:2 randomization (approximately 270 patients in the abemaciclib arm and 180 patients in the erlotinib arm). The final analysis will occur when approximately 304 OS events have been observed.

Assuming an OS HR of 0.72, this sample size yields approximately 80% statistical power to detect superiority of the abemaciclib arm over erlotinib arm with the use of a 2-sided log-rank test and a type I error of .05.

If the true median OS for the erlotinib arm is 6.5 months, then the HR of 0.72 amounts to an approximately 2.5-month improvement in median OS for the abemaciclib arm under an additional assumption of exponential survival distribution.

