# 12.2.14. Interim Analyses

### 12.2.14.1. Safety Interim Analyses

The DMC is responsible for providing external oversight of patient safety in Study JPBK independently of the Lilly study team and Lilly GPS.

During the study, safety interim analyses will be performed approximately every 6 months. The safety interim analyses will be conducted to evaluate the overall safety profile of abemaciclib. At the recommendation of the DMC, the frequency of safety interim analyses may be modified.

At each interim analysis, the DMC may recommend the trial continue without modifications, continue with specific modifications, or be stopped for safety concerns. There will be no prespecified rules for stopping the trial due to safety concerns. The DMC members will review unblinded safety data at each interim analysis. If a significant safety signal is identified, the DMC may recommend a protocol amendment, termination of enrollment, and/or termination of study treatment. The recommendations of the DMC will be communicated to the Lilly Senior Management Designee and, if necessary, an Internal Review Committee.

In the event that safety monitoring uncovers an issue that needs to be addressed by unblinding at the treatment group level, members of the DMC can conduct additional analyses of the safety data. Additionally, unblinding of a limited number of Lilly representatives external to the study team may be required for evaluation of selected SAEs for determination of regulatory reporting.

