### 12.2.14.2. Efficacy Interim Analyses

One interim efficacy analysis is planned based on the PFS endpoint. This interim analysis is for futility only and will be conducted by the DMC. There is no plan for interim efficacy analysis based on the OS endpoint. The DMC may call for additional, unplanned, interim efficacy analyses. Details of the DMC communication plan can be found in the DMC charter.

The interim efficacy analysis will be conducted after approximately 100 PFS events have occurred. This analysis will be based on the PFS endpoint and will be for futility only. The DMC will be instructed to recommend the study be stopped for futility if the observed hazard ratio for PFS (as calculated using a stratified Cox proportional hazards model) is greater than 0.95.

Only the DMC is authorized to evaluate unblinded interim efficacy and safety analyses. Study sites will receive information about interim results ONLY if they need to know for the safety of their patients.

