# 6. A Priori Statistical Methods

## 6.1. Determination of Sample Size

The primary objective of this study is to compare Abemaciclib versus erlotinib with respect to OS in patients with Stage IV NSCLC whose tumors have detectable *KRAS* mutations (specifically, in codons 12 and 13 of the KRAS oncogene) and who have progressed after prior platinum-based therapy and received 1 additional therapy which may include an immune checkpoint inhibitor and/or other anti-cancer therapy; or are not eligible for further chemotherapy

The study will enroll approximately 450 patients in 3:2 randomization (270 patients in the Abemaciclib arm and 180 patients in the erlotinib arm). The final OS analysis will occur when approximately 304 OS events have been observed.

The comparison of the OS distributions between treatment groups will be conducted using a stratified log-rank test adjusted by all stratification factors. Following statistical hypotheses about OS hazard ratio (HR) will be tested for Abemaciclib over erlotinib:

 $H_0$ :  $HR \ge 1$  (Abemaciclib arm not superior to erlotinib arm)

H1: HR < 1 (Abemaciclib arm superior to erlotinib arm)

Assuming an OS HR of 0.72, this sample size yields approximately 80% statistical power to detect superiority of the Abemaciclib arm over erlotinib arm with the use of a 2-sided log-rank test and a type I error of 0.05.

If the true median OS for the erlotinib arm is 6.5 months, then the HR of 0.72 amounts to an approximately 2.5-month improvement in median OS for the Abemaciclib arm under an additional assumption of exponential survival distribution.

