#### 6.2.16.2. Futility and Efficacy Interim Analyses

One interim efficacy analysis is planned based on PFS endpoint and is for futility only. This interim analysis will be conducted by the DMC. There is no plan for interim efficacy analysis based on the OS endpoint. The DMC may call for additional, unplanned, interim efficacy analyses. Details of the DMC communication plan can be found in the DMC charter. The analysis will occur after approximately100 PFS events have been observed. The DMC will be instructed to recommend stopping the study for futility if the observed hazard ratio for PFS (as calculated using a stratified Cox proportional hazards model) is greater than 0.95. Only the DMC is authorized to evaluate unblinded interim efficacy and safety analyses. Study sites will receive information about interim results ONLY if they need to know for the safety of their patients.

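### Does the stated 80% OS power need correcting because it leaves out the PFS futility look?

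*Protocol*

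**What the plan says.** Protocol 12.1 and SAP 6.1 give the same power statement: in the protocol's words, "this sample size yields approximately 80% statistical power to detect superiority of the abemaciclib arm over erlotinib arm", and in the SAP's words, "this sample size yields approximately 80% statistical power to detect superiority of the Abemaciclib arm over erlotinib arm". Both tie it to an OS hazard ratio of 0.72, about 304 OS events, 450 patients randomized 3:2, and a 2-sided log-rank test at 0.05. Neither section mentions an interim look.

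The look is described elsewhere. Protocol 12.2.14.2 reads "The DMC will be instructed to recommend the study be stopped for futility if the observed hazard ratio for PFS" and SAP 6.2.16.2 reads "The DMC will be instructed to recommend stopping the study for futility if the observed hazard ratio for PFS". In both, the threshold is an observed stratified Cox hazard ratio above 0.95, at about 100 PFS events. Both sections say the look is for futility only and that no OS interim is planned, and both leave DMC communication to the charter.

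Protocol 5.5 explains that PFS was dropped from the primary objective so that "all statistical power can be reallocated to enhance the success for OS". The current text states no PFS hazard ratio for this trial. The value 0.67 survives only as deleted text in the Amendment (e) summary (Attachment 10).

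**The concern.** OS is the sole primary endpoint, so its power is the central design figure. A futility rule can stop a trial of an effective drug, and every such stop takes away some chance of a positive OS result. The 80% figure uses up the 304 events exactly and leaves nothing to cover this.

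Amendment (e) makes the omission look worse. It gives OS all the alpha but keeps a stop driven by PFS, and it removes the PFS assumption from the sample-size section. The plan gives no stopping probability and does not say whether the rule is binding. A reader therefore cannot work out from the current text how often the whole procedure would succeed. If the PFS effect were weak while the OS effect was as hoped, the shortfall would be large.

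**Working it through.** **The plan's own figure.** Inputs from Protocol 12.1: 304 events, hazard ratio 0.72, allocation 0.6/0.4 (product 0.24), critical value 1.96.

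- Expected OS statistic: √(304 × 0.24) × |ln 0.72| = 8.542 × 0.3285 = 2.806.
- Power: Φ(2.806 − 1.960) = Φ(0.846) = 0.801.
- Events for 80%: (1.960 + 0.842)² / (0.24 × 0.3285²) = 303.1, rounded up to 304.

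The stated 80% and 304 are the single-look figures and both reproduce.

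**Chance of a wrong stop.** With 100 PFS events at 3:2, SE(log HR) = 1/√(100 × 0.24) = 0.204. For a true PFS hazard ratio h, P(stop) = Φ(−(ln 0.95 − ln h) × √24). At h = 0.67 this is Φ(−(−0.0513 + 0.4005) × 4.899) = Φ(−1.711) = 4.4%.

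**Power if the stop is always followed.** This is the bivariate normal probability of passing the look and then having an OS statistic above 1.96. The documents do not give the correlation of the two statistics, so 0 to 0.5 is assumed. At correlation 0 it is a product: at h = 0.67, 0.8012 × (1 − 0.0436) = 0.766.

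| True PFS HR | P(stop) | OS power, correlation 0 | OS power, correlation 0.5 |
|---|---|---|---|
| 0.60 | 1.2% | 79.2% | 79.8% |
| 0.67 (superseded design value) | 4.4% | 76.6% | 78.4% |
| 0.72 | 8.7% | 73.1% | 76.0% |
| 0.80 | 20.0% | 64.1% | 68.8% |

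The OS hazard ratio is 0.72 throughout. The unstratified SE is used, and a Cox model over 16 strata would carry slightly less information.

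**Which correlation is plausible.** Death counts as a PFS event, so zero is not realistic. A simulation used exponential margins, control medians of 6.5 months for OS and 2 months for PFS (the latter from superseded text), and an assumed uniform 30-month accrual. It gave correlations of about 0.20 to 0.36. In that range the analytic power at 0.67 is 77.2 to 77.8%; the simulation itself gave 77.0 to 77.8%.

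**Power once the look is passed.** Divide by the probability of passing. At 0.67 and correlation 0.5: 0.7836 / 0.9564 = 81.9%. At 0.72: 0.7600 / 0.9128 = 83.3%. At correlation 0 it stays at 80.1%.

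**What the rule buys.** For a drug with no PFS effect (h = 1), P(stop) = Φ(0.0513 × 4.899) = Φ(0.251) = 59.9%.

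**Type I error.** With no effect on either endpoint and the stop followed, the one-sided error at correlation 0 is 0.025 × (1 − 0.599) = 0.010. At correlation 0.5 it is 0.021. Both are below 0.025.

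**The case for a change.** The strongest argument for a change is that the size of the loss depends on a number the plan no longer states. The 0.67 is superseded, and nothing in the current text commits the sponsor to it. If the PFS effect only matched the OS target of 0.72, the loss would be about 4 to 7 points; at 0.80 it would be about 11 to 16. The DMC is given a numeric threshold, so treating its recommendation as merely advisory may be generous. One sentence would settle the matter at little cost.

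The arithmetic in that argument stands, as does the absence of any statement on whether the rule is binding. The step from there to a required change does not. The wording is an instruction to recommend, so a stop is not automatic. The 0.72 and 0.80 scenarios are not this trial's PFS assumptions in any version. Nor do the documents say whether the look was still ahead when 304 events was set. Amendment (e) postdates October 2016, against a planned first visit in September 2014, so the look may well have been passed, although the text still describes it prospectively. A printed stopping probability would then mislead.

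The phrase in Protocol 5.5 concerns the end of the co-primary alpha split (.005 and .045 in the superseded text). It promises nothing about futility.

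Two wording points nearby do not alter this. Protocol 9.5 says "Interim analyses will be carried out approximately every 6 months by an independent DMC (external to Lilly) to monitor safety and efficacy", while 12.2.14.1 says "During the study, safety interim analyses will be performed approximately every 6 months". The first can be read as a loose summary of the safety reviews and the PFS look together. Protocol 12.2.14.2 also allows that "The DMC may call for additional, unplanned, interim efficacy analyses". The plan attaches no boundary for benefit to such reviews, and they have no part in the power calculation.

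**Conclusion.** No change is needed. The 80% is correct for what it describes: the final OS log-rank test under the listed inputs. Leaving out the futility look is a gap in reporting, and a statistician can fill it under stated assumptions, as above.

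At the only PFS design value in the documents the gap is about 2 to 3 points below a figure given as approximate. That assumes the look was still ahead, the recommendation was always followed, and the correlation was about 0.2 to 0.36. If the look was passed or the recommendation set aside, 80% is not overstated. The loss is large only if the PFS effect is well short of the OS effect, and no document assumes that.

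The rule is a fair trade-off: about a 4% chance of stopping wrongly at a PFS hazard ratio of 0.67, against about a 60% chance of stopping early when there is no PFS effect. It does not raise type I error. A fuller power statement would have to rest on a deleted hazard ratio and an assumed correlation, and would leave the event target, the rule, the analysis and the conclusions unchanged.

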# 12.2. Statistical and Analytical Plans

# 12.2.1. General Considerations

Statistical analysis of this study will be the responsibility of Lilly.

Efficacy analyses will be based on the intention-to-treat (ITT) analysis set. This population is defined as all patients randomized to study treatment. Patients will be grouped according to randomized treatment.

Safety analyses will be based on the Safety Population, defined as all enrolled patients receiving at least 1 dose of any study drug. Patients will be grouped according to treatment received in Cycle 1.

Pharmacodynamic and/or tailoring biomarker analyses will be based on the subset of patients from the above populations from whom a valid assay result (according to laboratory guideline) has been obtained.

All tests of treatment effects will be conducted at a 2-sided alpha level of 0.05, unless otherwise stated. All confidence intervals (CIs) will be given at a 2-sided 95% level, unless otherwise stated.

Any change to the data analysis methods described in the protocol will require an amendment ONLY if it changes a principal feature of the protocol.

Before unblinding of the aggregate database, minor modifications or clarifications to the data analysis methods may be described and justified in the SAP. The assumptions for each statistical method will be evaluated. If there is violation of assumptions, alternative statistical methods

may be used. Any other change to the data analysis methods described in the protocol, and the justification for making the change, will be described in the CSR.

Additional exploratory analyses of the data will be conducted as deemed appropriate.

# 12.2.2. Patient Disposition

A detailed description of patient disposition will be provided. It will include a summary of the number and percentage of patients entered into the study, enrolled in the study, and treated as well as number and percentage of patients completing the study, or discontinuing (overall and by reason for discontinuation).

A summary of all important protocol deviations will be provided.

# 12.2.3. Patient Characteristics

Patient demographics including age, sex, screening height and weight, screening body mass index, and smoking status will be reported using descriptive statistics.

Baseline disease characteristics will be summarized by presenting frequency counts and percentages for pathological diagnosis (histological or cytological), disease stage, or performance status.

Patient preexisting condition, historical illness, and prior chemotherapy (including both cytotoxic and targeted agents) will be summarized by treatment arm.

# 12.2.4. Concomitant Therapy

Concomitant medication will be summarized by treatment arm in a frequency table listing the terms recorded on the eCRF.

### 12.2.4.1. Postdiscontinuation Therapy

The numbers and percentages of patients reporting postdiscontinuation therapies will be provided overall, by type of therapy (surgery, radiotherapy, or systemic therapy), and by drug name.

# 12.2.5. Treatment Compliance

The number of dose omissions, reductions, and delays, cycles received, and dose intensity will be summarized for all treated patients per treatment arm.

Treatment compliance information for abemaciclib or erlotinib will be collected through capsule (abemaciclib) or tablet (erlotinib) counts at each tumor assessment visit. The estimate of percent compliance will be given by:

Percent Compliance =  $\frac{\text{Actual cumulative dose taken}}{\text{Expected cumulative dose to be taken}} \times 100$ 

The actual cumulative dose taken will be determined based on counting the number of capsules returned at each visit and subtracting that number from the number of capsules dispensed. The

expected cumulative dose to be taken will be determined based on the assigned dose and taking into account any dose reductions or omissions.

# 12.2.6. Primary Outcome and Methodology

The primary endpoint of this study is OS.Overall survival duration is measured from the date of randomization to the date of death from any cause. For each patient who is not known to have died as of the data-inclusion cutoff date for a particular analysis, OS will be censored for that analysis at the date of last contact prior to the data inclusion cutoff date (contacts considered in the determination of last contact date include AE date, lesion assessment date, visit date, and last known alive date).

The comparison of each of the OS distributions between treatment groups will be conducted using a stratified log-rank test with the following stratification variables: number of prior chemotherapy regimens (1 versus 2), ECOG PS (0 versus 1), gender (male versus female), and *KRAS* mutation (G12C versus all others).

The Kaplan-Meier method (Kaplan and Meier 1958) will be used to estimate the OS survival curves as well as survival rates at 3, 6, 9, and 12 months for each treatment group. These rates will be compared based on a normal approximation for the difference between the arms.

The Cox proportional hazard model (Cox 1972) with treatment as a factor, stratified by the stratification factors used in the randomization (as per the primary analysis) will be used to estimate the HR and corresponding 95% CI.

# 12.2.7. Secondary Outcome and Methodology

The secondary objectives for this study are stated in Section 6.2.

Progression-free survival time is measured from the date of randomization to the date of investigator-determined objective progression as defined by RECIST v1.1, or death from any cause. Patients who have neither progressed nor died will be censored at the day of their last radiographic tumor assessment (if available) or date of randomization if no post initiation (that is, postbaseline) radiographic assessment is available. The detailed censoring rules for PFS are described in Table JPBK.12.1.

	Situation	Date of Progression or Censor	Outcome
1	No baseline tumor assessments	Date of Randomization	Censored
2	No post baseline assessments and no death	Date of Randomization	Censored
3	No documented progression and no death (with a post-baseline tumor assessment)	Date of last adequate tumor assessment	Censored
4	Patient lost to follow-up (or withdrew consent from study participation) before documented progression or death	Date of last adequate tumor assessment	Censored
5	Documented progression	Date of documented progression. If a tumor assessment was done on multiple days, use the earliest date for that visit.	Progressed
6	Death without documented progression	Date of death	Progressed
7	Death or documented progression immediately after missed ≥2 consecutive post-baseline tumor assessment visits	Date of last adequate tumor assessment before missed assessments or date of randomization, whichever is later	Censored

